10.6.4.3 Interim Analyses and Data Monitoring

No interim analysis is planned for this study.

10.6.4.4 Multicenter Studies

Prior to database lock, a review of the blinded data will be performed to determine the size of each center. If there are centers with a small number of randomized subjects, then these centers will be pooled in order for analyses to be carried out. The process of combining centers will be based on the ITT population, and same pooling will be repeated for PP population.

A small center is defined as a center which randomizes less than 12 subjects. First, centers will be sorted by latitude zone (based on geographic and climatic similarities), number of randomized subjects (descending order) and center number (ascending order). Pooling will start with combining the largest of the set of small centers of a latitude zone with the smallest center within the same latitude zone. If there is a further need to combine data (the size of the pooled centers includes less than 12 subjects), the next smallest center will be combined with the next largest of the small centers, until the criterion of a minimum of 12 subjects is met. The process will continue until all pooled centers have a minimum of 12 subjects within the same latitude zone. Any remaining small centers of a latitude zone will be pooled with the last pooled center within the same latitude zone. The pooled centers and the remaining original unpooled clinical centers will be referred to as 'analysis centers' and will be used as stratification factor in the statistical analyses.

If at the start of pooling any latitude zone has less than 12 subjects in the ITT population in total, then centers will be added to the list of small centers in another latitude and then combined as above. This decision will be documented in clinical report.

Statistical Analysis Plan

The consistency of the treatment effect across analysis centers for the primary endpoint will be evaluated using graphical methods (Forest plot).

10.6.4.5 Multiple Comparison/Multiplicity

In order to maintain the overall type I error rate at 0.00125, a predefined hierarchal testing procedure will be implemented to test the MAL cream against vehicle.

Testing will start from primary endpoint and descend in the order described as below for the secondary endpoints until the null hypothesis fails to be rejected at 0.00125 level of significance.

1. Lesion complete response, defined as the percent reduction from baseline in the number of cleared treated lesions, at 12 weeks after the last DL-PDT treatment (Visit 6), comparing MAL cream with vehicle cream.
2. Subject partial response, defined as the proportion of subjects with 75% or greater reduction from baseline in the number of cleared treated lesions, at 12 weeks after the last DL-PDT treatment (Visit 6), comparing MAL cream with vehicle cream.

10.6.4.6 Use of an Efficacy Subset of Patients

The classification of the protocol deviations and the exclusion of subjects from the PP population will be determined prior to breaking the study blind (see section 8.3).

The analysis on the PP population will allow evaluating the impact of major protocol deviations on the estimation of the treatment effect.

10.6.4.7 Active-Control studies intended to show equivalence

Not applicable.

10.6.4.8 Examination of Subgroups

All subgroup analyses are exploratory in nature.

To determine whether the treatment effect is consistent across various subgroups, the estimate of the between-treatment effect (with nominal 99.875% and 95% CI) for primary endpoint and secondary endpoints will be presented within each category of the following classification variables:

- AK lesions location
 - ✓ Face
 - ✓ Balding scalp
- Baseline AK grade
 - ✓ Grade 1 (mild) AK
 - ✓ Grade 2 (moderate) AK
- Sex
 - ✓ Male
 - ✓ Female
- Number of baseline AK lesions
 - ✓ 4-8 AK lesions
 - ✓ 9-12 AK lesions

Statistical Analysis Plan

- Fitzpatrick skin type
 - ✓ Type I, II and III
 - ✓ Type IV, V and VI

Differences in proportions and their nominal 99.875% and 95% confidence intervals by category for the classification variables listed above will be reported as well as presented graphically (Forest plot) on the ITT population.

Missing data will be imputed using the same methods foreseen for the primary analysis of the primary endpoint and for the analysis of the secondary endpoints (see section 10.6.4.2).

10.6.4.9 Analysis Visits Definition

Efficacy, safety and other variables will be summarized and analyzed by analysis visit. Analysis visit will be slotted according to the following table (see Table 9) to summarize the data by proper visit.

Table 9 - Analysis Visits Definition

Clinical Visit	Analysis Visit	Analysis Visit Number	Target Study Day
Visit 1	Baseline	1	1
Visit 2	Baseline	1	1
Visit 2b	Baseline	1	1
Visit 3	Week 1	2	8
Visit 4	Week 2-4	3	15
Visit 4b	Week 2-4	3	15
Visit 5	Week 3-5	4	22
Visit 6	Week 14/Final	5	99
Early Termination	Early Termination	6	---

Visit 2b and Visit 4b will occur only in case of incomplete treatment at Visit 2 and Visit 4 respectively. All efficacy assessments performed on Visits 2b and 4b will be assumed to fall at Visits 2 and 4 regardless of actual time.

Early termination visit assessments will be summarized as a separate visit in all by-visit outputs.

Unscheduled visits will be assigned to the same analysis visit of the last scheduled visit (including re-treatment visits) that occurred before the unscheduled visits.

All post-baseline safety assessments will be used for potentially clinically significant value (PCSV) determinations.

For efficacy and safety endpoints, if two or more assessments (include both scheduled and unscheduled assessments) are available for the analysis visits then all assessments will be listed and the following rules will be applied for determining the values to be used for the summary and analyses.

For efficacy endpoints:

Statistical Analysis Plan

- **Baseline Analysis Visit:** in presence of multiple assessments, the last assessment performed before the first DL-PDT treatment (regardless of treatment completion status) will be used for the summaries and analyses.
- **Week 2-4 Analysis Visit:** in presence of multiple assessments, the first assessment performed after the first DL-PDT will be used for the summaries and analyses.
- **Week 14/Final Analysis Visit (where applicable):** in presence of multiple assessments, the first assessment performed after the last DL-PDT will be used for the summaries and analyses.

For safety assessments:

- **Clinical Laboratory Evaluation:** in presence of multiple assessments on an analysis visit, the latest assessment will be used for the summaries and analyses.
- **Vital Signs, ECG, Physical Examination:** in presence of multiple assessments on an analysis visit, the assessment closest to the target visit date will be used for the summaries and analyses.
- **Pain Assessment:** in presence of multiple assessments on an analysis visit, the worst assessment (i.e. the one with the higher NRS score) will be used for the summaries and analyses.

For other assessments:

- **Satisfaction Questionnaire:** in presence of multiple assessments on an analysis visit, the first assessment performed after the last DL-PDT will be used for the summaries and analyses.

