10 STATISTICAL METHODS AND DATA CONSIDERATIONS

10.1 General Considerations

10.1.1 Baseline

For statistical analyses purpose, baseline is defined as the last measurement prior to the first DL-PDT treatment (regardless of treatment completion status).

Change from baseline and percent change from baseline will be calculated as:

Change from Baseline = PostBaseline Value – Baseline Value

$$\text{Percent Change from Baseline} = \begin{cases} \text{Baseline Value} \neq 0 \Rightarrow 100 \cdot \frac{\text{PostBaseline Value} - \text{Baseline Value}}{\text{Baseline Value}} \\ \text{Baseline Value} = 0 \Rightarrow \text{Missing} \end{cases}$$

Statistical Analysis Plan

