10.1.3 Reference Start Date and Analysis Day

The first study treatment date will be the reference start date.

Analysis day will be calculated from the first study treatment date and will be used to show start/end day of assessments, events, therapies or procedures.

Statistical Analysis Plan

In the situation where the assessment/event/therapy/procedure/disease date is fully missing and cannot be imputed (i.e. when event, therapy or procedure is reported as being ongoing), analysis day will be missing.

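### SAP 10.6.4.9 conflicts with SAP 10.1.1 on the safety baseline: its selection rules have no pre-treatment limit, so if followed they can make a post-treatment unscheduled value the Baseline value

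*SAP*

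**What the plan says.** SAP 10.1.1, under General Considerations, states that "baseline is defined as the last measurement prior to the first DL-PDT treatment (regardless of treatment completion status"). It then introduces the change formulas: "Change from baseline and percent change from baseline will be calculated as".

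SAP 10.6.4.9 assigns assessments to analysis visits. Table 9 puts Visits 1, 2 and 2b in Baseline with target Study Day 1, and Visit 3 in Week 1 with target Day 8. For other contacts, "Unscheduled visits will be assigned to the same analysis visit of the last scheduled visit (including re-treatment visits) that occurred before the unscheduled visits". Where an analysis visit holds several assessments, scheduled or unscheduled, "the following rules will be applied for determining the values to be used for the summary and analyses". Those rules are:

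- Efficacy, Baseline: "the last assessment performed before the first DL-PDT treatment (regardless of treatment completion status) will be used for the summaries and analyses".
- Laboratory: "in presence of multiple assessments on an analysis visit, the latest assessment will be used for the summaries and analyses".
- Vital signs, ECG, physical examination: "the assessment closest to the target visit date will be used for the summaries and analyses".

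SAP 6.2.5 to 6.2.8 schedule these four safety assessments only at screening and Visit 6/ET, but allow them at any unscheduled visit. Protocol 8.6 defines unscheduled visits as those for repeating abnormal laboratory tests or following up AEs.

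**The concern.** Only the efficacy rule repeats the pre-treatment limit. Read literally, the slotting rule sends an unscheduled safety assessment made after the first DL-PDT to Baseline, and the safety rules can then prefer it to screening. Section 10.1.1 forbids that result. The SAP does not say which section takes precedence, so the outcome depends on which one the programmer follows.

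The values at risk are not a random set. Unscheduled visits exist to chase abnormal results and AEs, so a displacing value may be a post-treatment abnormality shown as already present at baseline. The outputs exposed are:

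- the Baseline columns of the safety tables (SAP 10.7.4 to 10.7.7);
- laboratory and vital-sign change from baseline;
- the laboratory shift tables;
- the vital-sign PCSV criteria in Table 10, each of which requires a change relative to baseline.

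**Working it through.** The plan gives no figure to reproduce, so the check applies the rules literally. Day 1 is the actual first treatment date, because "The first study treatment date will be the reference start date".

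**1. How long the Baseline slot stays open after treatment.** It closes the day before Visit 3. Inputs: Visit 3 target Day 8 (Table 9), window -2 to +14 days, and retreatment at Visit 2b after at most 4 weeks (SAP Table 1 and footnote b).

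- Visit 3 at -2 days: 8 - 2 - 1 = Day 5.
- Visit 3 on target: 8 - 1 = Day 7.
- Visit 3 at +14 days: 8 + 14 - 1 = Day 21.
- Visit 2b on Day 29, Visit 3 one week later at +14 days: 29 + 7 + 14 - 1 = Day 49. This needs a rained-out session, the longest retreatment interval and the latest Visit 3 together.

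**2. Laboratory tests.** The latest value in the slot is taken. For any analyte retested after the first DL-PDT and before Visit 3, that is the post-treatment value. An analyte not retested keeps its screening value; Protocol 8.6 does not require every procedure at an unscheduled visit.

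**3. Vital signs, ECG, physical examination.** Let s be the number of days from the nearest pre-treatment value to Day 1. A post-treatment value on Day d lies d - 1 days from Day 1 and is chosen when d - 1 < s, that is, when d is at most s. At d = s + 1 there is a tie, for which the SAP has no rule.

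- Screening is the only pre-treatment value, s = 5 (the minimum in SAP Table 1): chosen on Days 2 to 5, tie on Day 6.
- Screening only, s = 14: chosen to Day 14 while the slot is open.
- Screening only, s = 14 + 14 = 28: chosen to Day 28 while the slot is open. This assumes that screening was timed to the planned Visit 2, which then slipped by the full 14 days; no section states that the two windows add.
- A pre-treatment unscheduled repeat 2 days before Day 1 (hypothetical): it also falls in Baseline, following Visit 1. Then s = 2, and a post-treatment value is chosen on Day 2 only, with a tie on Day 3.

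**4. Effect on one subject.** Hypothetical systolic pressure: 130 mmHg at screening, 165 on Day 3 (distance 3 - 1 = 2, less than 5), 165 at Visit 6. Table 10 requires at least 160 mmHg and an increase of at least 20.

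| | If 10.1.1 governs | If 10.6.4.9 governs |
|---|---|---|
| Baseline | 130 | 165 |
| Change at Visit 6 | 165 - 130 = +35 | 165 - 165 = 0 |
| Table 10 flag at Visit 6 | yes | no |
| Status of the Day 3 value | post-baseline | Baseline |

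**5. Effect on a group mean.** The documents give no frequency. Assume that 0.5% to 2% of the 380 MAL subjects are displaced, each by 35 mmHg. That is 380 x 0.005 = 1.9 to 380 x 0.02 = 7.6 subjects, and the Baseline mean moves by 35 x 0.005 = 0.18 to 35 x 0.02 = 0.70 mmHg. On that assumption any visible effect is on individual values and category counts, not on means.

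**The case against.** The best reply is that 10.1.1 already governs. It sits under General Considerations, defines baseline for statistical analysis generally and is not confined to efficacy. The safety sections report results at baseline, which is the term it defines. On that reading, 10.6.4.9 only chooses among assessments that are already eligible. Protocol 10.1.4.3 points the same way by stating that baseline laboratory samples are taken before study drug. SAP 10.6.4.9 also uses all post-baseline safety assessments for PCSV determination, and under 10.1.1 a post-treatment value is post-baseline.

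Much of this stands, and it makes every consequence conditional. A reader might infer that the Baseline columns are wrong on any reading and that only change, shift and PCSV outputs depend on precedence, so that one table must mix two baselines. The documents do not support that: 10.1.1 defines baseline itself, not just the change formulas, and if it governs it can govern the columns too.

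The reply does not remove the conflict. The label Baseline in Table 9 does not imply pre-treatment: pain is scored after illumination at Visits 2 and 2b (SAP 6.2.1), and both visits are slotted there. The efficacy rule restates the limit, while the adjacent safety rules omit it. And 10.6.4.9 is the more specific text on which value is used. The shells that will carry the code (SAP 12 and 13.1) are a separate document, so they cannot be consulted here.

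**Conclusion.** The conflict is real and the correction is minor. If 10.6.4.9 is programmed as written, a post-treatment value becomes Baseline for any laboratory analyte retested between the first DL-PDT and Visit 3. For vital signs, ECG and physical examination it does so when it is nearer to Day 1 than every pre-treatment value. The safety Baseline columns, laboratory and vital-sign change, laboratory shifts and the Table 10 change criteria would then be wrong for those subjects. If 10.1.1 governs, none of these is affected.

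Two further inferences go too far. Displacement is not certain on Days 2 to 5 for everyone, because a pre-treatment repeat may lie closer to Day 1 than screening does. Nor would safety signals be lost: Protocol 9.2.5 and 9.2.7 to 9.2.9 have clinically significant findings recorded as AEs, judged against screening for laboratory values, vital signs and physical examination, and 10.6.4.9 lists all assessments.

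The number of subjects is not given and is probably small, since it is limited to those with an unscheduled assessment in this interval. SAP 10.7 plans no safety inference. Efficacy, AE reporting and listings are unaffected.

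**What to change.** Add to SAP 10.6.4.9: for laboratory tests, vital signs, ECG and physical examination, the Baseline value is the last assessment before the first DL-PDT, as in 10.1.1; unscheduled assessments after the first application are post-baseline, including for PCSV determination. The cost is one sentence and a small change to the derivation, with no additional data collection.

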## 8.6 Unscheduled Visit

The subject should be reminded to adhere to the study schedule. Unscheduled visits are defined as visits to repeat testing for abnormal laboratory results or for follow-up of AEs. Visits occurring outside of the visit window are not considered unscheduled visits.

Assessments to be conducted at the unscheduled visit will depend on the reason for the visit and will be conducted at the discretion of the principal investigator. Any of the procedures/assessments listed in [Section 8.1.2](#) may be conducted, but not all are required.

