#### **9.2.5 Clinical Laboratory Evaluation**

---

The hematology laboratory analyses, clinical chemistry laboratory analyses, and urinalyses will be performed at a central laboratory. Reference ranges will be supplied by the central laboratory and used by the Investigator to assess the laboratory data for clinical significance and pathological changes.

The Investigator or medically-qualified sub-investigator must review and evaluate laboratory values for each subject in a timely manner. Study centers should refer to the current version of the laboratory manual for laboratory values outside of normal limits. For each out-of-range laboratory result, the Investigator or designee will evaluate whether he/she considers it to be clinically significant (CS), defined as meeting at least 1 of the following conditions:

- The abnormality suggests a disease and/or organ toxicity, or
- The abnormality is of a degree that requires additional active management, e.g., discontinuation of the drug, close observation, more frequent follow-up assessments, or further diagnostic investigation.

If the Investigator observes a CS laboratory result, the test will be repeated as soon as possible and the subject will be monitored until the value returns to normal and/or an adequate explanation for the abnormality is found.

Investigators will also be allowed to repeat specific laboratory test(s) or procedure(s) where he/she suspects an inaccuracy or false result, and which may impact the safety of the subject or the interpretation of the study results; only after discussion with the medical monitor.

All CS out-of-range laboratory values at the screening visit will be recorded (report a diagnosis rather than the laboratory value, whenever possible). All CS out-of-range laboratory values after the screening visit are to be reported as an AE if this abnormality was not present at the screening visit or is assessed as having worsened since the screening visit (i.e., changed significantly from the screening visit). Whenever possible, the Investigator should provide a diagnosis of an AE when reporting the abnormal laboratory value.

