6.2.5 Clinical Laboratory Evaluation

The hematology laboratory analyses, clinical chemistry laboratory analyses, and urinalyses will be performed at a central laboratory. Samples for the analyses will be collected at screening visit and visit 6/ET and/or at any unscheduled visit. Reference ranges will be supplied by the central laboratory and used by the investigator to assess the laboratory data for clinical significance and pathological changes.

The Investigator or medically-qualified sub-investigator must review and evaluate laboratory values for each subject in a timely manner. Study centers should refer to the current version of the laboratory manual for laboratory values outside of normal limits. For each out-of-range laboratory result, the Investigator or designee will evaluate whether he/she considers it to be clinically significant (CS), defined as meeting at least 1 of the following conditions:

- The abnormality suggests a disease and/or organ toxicity, or
- The abnormality is of a degree that requires additional active management, e.g., discontinuation of the drug, close observation, more frequent follow-up assessments, or further diagnostic investigation.

If the Investigator observes a CS laboratory result, the test will be repeated as soon as possible and the subject will be monitored until the value returns to normal and/or an adequate explanation for the abnormality is found.

Investigators will also be allowed to repeat specific laboratory test(s) or procedure(s) where he/she suspects an inaccuracy or false result, and which may impact the safety of the subject or the interpretation of the study results; only after discussion with the medical monitor.

All CS out-of-range laboratory values at the screening visit will be recorded (report a diagnosis rather than the laboratory value, whenever possible). All CS out-of-range laboratory values after the screening visit are to be reported as an AE if this abnormality was not present at the screening visit or is assessed as having worsened since the screening visit (i.e., changed significantly from the screening visit). Whenever possible, the Investigator should provide a diagnosis of an AE when reporting the abnormal laboratory value.

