10.7.6 Clinical Laboratory Tests Analysis

Descriptive statistics (n, mean, standard deviation, median, first and third quartile, min and max) by treatment group and overall will be presented for blood chemistry, hematology and quantitative urinalysis parameters at baseline and visit 6/ET and for their change from baseline to visit 6/ET.

Statistical Analysis Plan

For summary purposes, laboratory values that are listed as above or below particular thresholds will be numerically imputed as above or below that threshold, respectively, by the minimum measured amount for that parameter. For example, if a parameter is measured to two decimal places, and has a result of "> 5" then, for summary purposes, the value of 5.01 will be used.

Number and percentage (n, %) of subjects for each response category of qualitative urinalysis parameter will be presented by treatment group and overall at baseline and visit 6/ET.

Number and percentage (n, %) of subjects with laboratory test values below, within and above the laboratory reference ranges will be summarized by treatment group and overall at baseline and visit 6/ET.

Number and percentage (n, %) of subjects with Clinically Significant Abnormal Values (as identified by the Investigator) and with Potentially Clinically Significant Values (see section 13.3) will be summarized by treatment group and overall at baseline and visit 6/ET.

Shift tables from baseline to visit 6/ET describing shifts to abnormality will be provided as well. Only subjects with a baseline result and a result at visit 6/ET for the parameter will be considered.

A listing of all clinical laboratory test will be provided.

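### The latest-value rule for laboratory data tends to replace an abnormal scheduled Visit 6 result with its retest in the change, reference-range and shift tables

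*SAP*

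**What the plan says.** **Sampling.** The schedules of assessments (Protocol Table 3, SAP Table 1) place blood and urine tests at screening and Visit 6/ET only. SAP 6.2.5 adds samples taken at any unscheduled visit.

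**Retesting.** Protocol 9.2.5: "If the Investigator observes a CS laboratory result, the test will be repeated as soon as possible". SAP 6.2.5 has the same rule, with its end point: "the test will be repeated as soon as possible and the subject will be monitored until the value returns to normal and/or an adequate explanation" is found. Protocol 8.6: "Unscheduled visits are defined as visits to repeat testing for abnormal laboratory results or for follow-up of AEs".

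**Assignment to an analysis visit.** SAP 10.6.4.9: "Unscheduled visits will be assigned to the same analysis visit of the last scheduled visit (including re-treatment visits) that occurred before the unscheduled visits". Scheduled and unscheduled values then compete: "if two or more assessments (include both scheduled and unscheduled assessments) are available for the analysis visits then all assessments will be listed", and one is chosen for the tables. For laboratory data, "in presence of multiple assessments on an analysis visit, the latest assessment will be used for the summaries and analyses".

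**Output.** SAP 10.7.6 plans descriptive statistics and change from baseline, counts below, within and above the reference range, counts of investigator-identified CS values and of PCSVs, and shift tables: "Shift tables from baseline to visit 6/ET describing shifts to abnormality will be provided as well".

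**Exception.** SAP 10.6.4.9 also says that PCSV determinations draw on every post-baseline safety assessment, while 10.7.6 counts PCSVs at baseline and Visit 6/ET.

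**The concern.** Whether a second laboratory value exists at Week 14/Final depends largely on the first one. A CS result must be repeated; a normal result need not be. A rule that always takes the later record therefore acts mostly on subjects who had an abnormal finding, and shows how the finding ended rather than that it occurred.

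Visit 6/ET is the only scheduled laboratory sample after treatment. A shift table is meant to show who moved from normal to abnormal by then. If transient CS abnormalities drop out, the arm with more of them loses more, and the between-arm comparison is pulled towards no difference.

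The SAP does not take this approach elsewhere. Section 10.6.4.9 uses the first assessment after the last DL-PDT session for Week 14/Final efficacy, the one closest to the target date for vital signs, ECG and physical examination, and the worst score for pain.

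**Working it through.** The documents state no figure for this point, so there is none to reproduce. The check follows one result through the rules.

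**Chain of rules**

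1. The Visit 6 result is out of range and judged CS. A repeat is required (Protocol 9.2.5, SAP 6.2.5).
2. The repeat takes place at an unscheduled visit (Protocol 8.6).
3. The last scheduled visit before it is Visit 6, so the repeat falls in Week 14/Final (SAP 10.6.4.9, Table 9).
4. Two values now sit in that analysis visit, and the latest is used.
5. The Visit 6/ET tables in SAP 10.7.6 are built from the selected value. No sentence exempts the change, reference-range or shift tables, and none exempts the investigator-identified CS count.

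**Example (assumed values).** ALT, ULN 40: screening 30; Visit 6 on day 99, 100, judged CS; retest on day 106, 35.

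| Rule | Value used | Shift | Change from 30 |
|---|---|---|---|
| Latest (SAP, laboratory) | 35 | normal to normal | 35 − 30 = +5 |
| First (SAP, efficacy at Week 14/Final) | 100 | normal to high | 100 − 30 = +70 |
| Closest to day 99 (SAP, vital signs and ECG) | 100 | normal to high | +70 |
| Worst (SAP, pain) | 100 | normal to high | +70 |

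The closest rule keeps the scheduled value whenever Visit 6 falls on or after day 99, because the retest is later still.

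**Does the PCSV count catch it?** The ALT criterion in SAP Table 11 is above 3 × ULN, here 3 × 40 = 120. The Visit 6 value is 100 / 40 = 2.5 × ULN, so no PCSV is set. A value of 150 would be flagged under 10.6.4.9 whatever the retest showed. Table 11 has no criterion at all for INR, direct bilirubin, total protein, red cell count, mean cell volume or any urinalysis parameter, although SAP 6.2.5.1 to 6.2.5.3 list them as collected.

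**Possible size.** The documents give no rate of CS results or of normalisation, so both are assumed. The plan's 7% non-evaluable rate for the primary endpoint serves as a stand-in for missing Visit 6 samples: 380 × 0.93 = 353.4 MAL subjects.

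| Assumed CS rate at Visit 6 | Subjects with a CS value | Replaced if 25% normalise on retest | Replaced if all do |
|---|---|---|---|
| 1% | 3.5 | 0.9 | 3.5 |
| 5% | 17.7 | 4.4 | 17.7 |

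Some of these subjects would still be counted as PCSVs, so the table is an upper view of what the summaries lose.

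**The case against.** **Other outputs catch much of this.** PCSV determinations use all post-baseline values, new or worsened CS results are reported as adverse events and tabulated by arm, and every value is listed. Out-of-range values not judged CS need no repeat and generally stay in the tables. This stands, and it confines the loss mainly to CS values short of a PCSV criterion. It does not remove the loss: adverse events are preferably recorded as a diagnosis, which does not restore the analyte-level shift, and listings do not compare arms. The PCSV protection also depends on 10.6.4.9 prevailing over the visit-specific wording of 10.7.6.

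**The rule is not one-way.** A reader might infer that CS results are retested until normal and that replacement works only towards normality. The documents do not support either. Monitoring may end with an explanation while the value is still abnormal. Repeats for suspected inaccuracy (after discussion with the medical monitor), samples at adverse event follow-up and medically indicated samples can replace a value in either direction. What remains is a tendency, because only the CS result carries a duty to repeat.

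**Latest is a legitimate prespecified choice.** It ignores treatment arm, and where the first result was false the later one is better. That is a reason to use a retest when the scheduled sample is invalid, not in every case.

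**Conclusion.** The point holds as a tendency with limited reach. As written, a CS result at Visit 6 that normalises on retest is represented by the retest in the change-from-baseline, reference-range and shift tables, and possibly in the investigator-identified CS count. This assumes that retests made after Visit 6 reach the analysis database, which SAP 6.2.5 implies by counting unscheduled samples among those for analysis.

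A reader might conclude that abnormal laboratory findings vanish from the report, including elevations above 3 × ULN. They do not: under 10.6.4.9 such an ALT value is still a PCSV, and new or worsened CS values are still adverse events.

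The size is unknown. The assumed rates above give between about 1 and 18 MAL subjects before allowing for those counted as PCSVs, and the true number is probably small. SAP 10.7 plans no formal inference on safety data, and no efficacy endpoint is involved. This is a minor matter and a cheap improvement.

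**What to change.** 1. In SAP 10.6.4.9, replace the laboratory rule for post-baseline summaries and shift tables: use the scheduled Visit 6/ET sample, and a retest only if that sample is missing or invalid, including a result confirmed as false.
2. In SAP 10.7.6, add a worst-post-baseline shift table and a CS count that include unscheduled results.
3. Reconcile the PCSV wording: 10.6.4.9 uses all post-baseline assessments, while 10.7.6 counts at baseline and Visit 6/ET. State which values feed the PCSV table.

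The cost is a sentence or two in the SAP, a small derivation change and at most one extra table. Data collection and retesting practice stay as they are.
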